6. STUDY PROCEDURES

6.1 Screening and Enrollment

6.1.1 Screening for Eligibility

As shown in the Figure 2, potential participants in this study will contact the research team at each MTF through physician or self-referral. All referrals will be asked to talk to the Research Coordinator at the local study site. Potential participants can self-refer through the website, www.prioriti-mtf.org. A screening CRF will be completed on every potentially eligible participant and entered into REDCap, the METRC electronic data capture system in order to document screen failures.

At the time of initial screening, the Research Coordinator will describe the study and if the patient is still interested, will obtain oral consent to conduct a brief telephone screen. The interview will consist of the following:

- Questions about the injury and its initial treatment to confirm the individual is 1 or more years out from a traumatic injury of the lower extremity (at or below the knee) (to include: cause of the injury, when it occurred, where the person was hospitalized and for how long and a description of the injury);
- The Short Form Musculoskeletal Function Assessment (SMFA) to determine whether the individual is impaired or bothered by their level of function due to their leg injury.

[figure not shown]

Figure 2

Individuals meeting the initial screening criteria will be mailed a consent form and will receive a follow up phone call within 5 business days. If at that time the patient decides to participate, the Research Coordinator will schedule an appointment to come to the study center for testing and final screening to confirm that the patient meets the final inclusion/exclusion criteria for the

study. The final (in person) screen will consist of a clinical assessment, medical history, and interview.

6.1.2 Consent and Enrollment

A prototype consent has been prepared for the PRIORITI study and is attached in Appendix D. Individual sites may add material but may not delete material thought to be necessary for informed consent. Clinical sites may reformat and reword information to conform to their local requirements. The consent form will describe the purpose of the study, the procedures to be followed, and the risks and benefits of participation. Copies of the signed consent forms will be given to the patient, and this fact will be documented in the patient's record.

Informed consent will take place at the study center before beginning the final in-person screen. The conversation will be initiated by the Research Coordinator and surgeon investigator together. Patients will be provided a pamphlet describing the study, the risks and benefits of participation and what will be expected of them if they choose to participate. After reviewing all components of the informed consent form, the surgeon investigator and the Research Coordinator will answer any questions the patient has about participating in the study. Consent will be obtained in accordance with principles of GCP and ICH guidelines.

Following completion of informed consent, the surgeon investigator will conduct a clinical assessment, medical history, and interview to confirm eligibility. Patients who are ineligible will not continue in the study and will be withdrawn.

All patients must be able to provide informed consent; there will be no consent by Legally Authorized Representatives.

All study materials will be provided in English.

Additionally, after completion of informed consent, the participant information will be entered into REDCap where a study number will be assigned and final eligibility criteria confirmed.

6.1.3 Assessing Capacity to Consent and Consenting a Proxy Respondent

N/A

6.1.4 Informed Consent Process or Assent (for a minor)

N/A

6.2 Baseline Data Collection

Once consented into the study, baseline data regarding participant characteristics, injury characteristics, fracture classification and medical history/co-morbidities will be collected and entered into the REDCap data collection system. An x-ray will be obtained to confirm healing of the fracture and to identify presence of post-traumatic osteoarthritis. This x-ray will be used to confirm suitability of the IDEO for the individual. If, based on the x-ray, a decision is made that

the patient is *not* suitable to receive the intervention, he or she will be withdrawn from the study. Participants who remain eligible will complete a performance assessment and a brief interview.

For patients treated acutely (initially at the time of the injury) in an institution other than the recruiting institution, permission will be sought from the participant to access the medical records pertaining to the initial hospitalization.

The data collected at baseline are described below. These data are summarized in Appendix C.

6.2.1 Baseline Clinical Assessment and Medical History

- Study Injury Characteristics
 - Mechanism, Type, Side of Injury
 - Classification of Fracture (AO/OTA and Gustilo)
 - Presence of other limb and non-limb injuries (ICD-9CM codes)
- Current Limb Status
 - ROM and Strength of study limb
 - Radiographic Evaluation of Healing (from x-ray)
 - Evidence of PTOA (from x-ray)
 - VAS Pain and Use of Narcotics
- Height and Weight
- Co-morbidities
- Smoking History

6.2.2 Performance Assessments

- 4 Square Step Test
- Illinois Agility Test
- Sit to Stand
- Timed Stair Ascent
- Self Selected Walking Speed
- Shuttle Run
- Single Leg Stance

6.2.3 Participant Interview

- Age, gender, race and ethnicity, education, and income (past year)
- Marital status
- Usual major activity status
- If working, what type of work and physical demands of the job; Work Productivity (WPAI)
- Job Motivation
- Multidimensional Scale of Perceived Support (MSPS)
- Health insurance
- Self Efficacy to perform major usual activity
- Short Musculoskeletal Function Assessment (SMFA)
- Veterans Health Survey (VR-12)
- Paffenbarger Activity Scale (PPAQ)

- Brief Pain Inventory (BPI)
- Patient Health Questionnaire Dépression Scale (PHQ-9)
- Post Traumatic Stress (PCL Checklist)
- Shoe Wear and Use of Ambulatory Aids
- Hospitalizations in Past Year
- Use of Orthotic Services in Past Year
- Use of PT/OT Services in Past Year
- Use of Other Services Related to the Injury in Past Year

If, during the course of completing the PHQ-9 or PCL via participant self-report survey or interview, a participant has a PHQ-9 score indicating major depressive disorder (≥ 20) or has a PCL score indicating clinically significant PTSD (≥ 30), the participant will be notified and advised to contact his/her physician or to visit the emergency department.

If on the PHQ-9 item #9, the participant reveals that he/she has thoughts of being better off dead or of hurting themselves in any way, more often than “not at all,” the coordinator will ask the following questions to the participant:

1	Interviewer:	Let me ask another question, have you thought of hurting yourself in any way?
	Participant:	Yes No If no: “It is difficult having thoughts like this. You should talk to your doctor about these thoughts, as you may benefit from treatment for depression.” Continue with interview. If yes: Continue with following questions.
2	Interviewer:	Does your doctor know about this?
	Participant:	Yes No If yes: “It is difficult having thoughts like this. You should talk to your doctor about these thoughts, as you may benefit from treatment for depression.” Continue with interview. If no: Continue to following questions.
3	Interviewer:	Have you talked to another clinician, like a counselor or psychologist, about how you have been feeling lately?
	Participant:	Yes No If yes: “It is difficult having thoughts like this. You should talk to your doctor about these thoughts, as you may benefit from treatment for depression.” Continue with interview. If no and if in-person: “I am not a clinician, but we want a clinician on the

study to talk with everyone who tells us they have been feeling this way recently. I would like Dr. _____ or Dr. _____ to speak with you today. If you are having thoughts of hurting yourself, the best thing to do is to go to the emergency department or call the National Suicide Prevention [contact]).”

If no and if on phone: “I am not a clinician, but we want a clinician on the study to talk with everyone who tells us they have been feeling this way recently. I would like [name] to give you a call today or tomorrow. If you are having thoughts of hurting yourself, the best thing to do is to go to the emergency department or call the National Suicide Prevention [contact]).”

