- **Pain** will be measured using the Brief Pain Inventory (BPI). The BPI is a widely used, 15-item measure of pain intensity and interference with daily life ⁷⁶. The questionnaire assesses three key pain domains: pain intensity, pain interference, and efficacy of pain treatments or medications. It has been extensively validated in both English and Spanish. Overall study limb as well as knee and ankle specific pain intensity will be measured using the 0-10 visual analogue scale used in the Brief Pain Inventory. Pain intensity will be measured both at rest and during ambulation. The BPI pain intensity domain is compatible with the IMMPACT guidelines for assessing pain in clinical trials and the FDA Guidance for Industry on the use of Patient-Reported Outcome Measures ⁷⁷. At each clinical follow up, the treating surgeon will also record the type (grouped as acetaminophen, opioids, GABA analogues (like Neurontin or Lyrica), and NSAIDs (like Ibuprofen or Naproxen), and other) and frequency of pain medication use.
- **Depressive Symptoms** will be assessed using the nine item depression scale of the Patient Health Questionnaire (PHQ-9) ⁷⁸. The PHQ-9 is a well validated tool for assisting clinicians in diagnosing depression. There are two components of the PHQ-9: (1) assessing symptoms and functional impairment to make a tentative depression diagnosis, and (2) deriving a severity score. The PHQ-9 is based directly on the diagnostic criteria for major depressive disorder in the Diagnostic and Statistical Manual Fourth Edition (DSM-IV).
- **Post Traumatic Stress (PTSD)** will be measured using the standard PTSD Checklist (PCL), a 17-item measure that elicits responses for each of the DSM-IV disorders that comprise the diagnostic criteria for PTSD (intrusive, avoidant, and arousal symptoms) ⁷⁹. The psychometric properties of the PCL have been well established and it is the most widely used measure of PTSD. Both civilian and military versions are available.

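### In the PHQ-9 item 9 script, a participant who confirms self-harm thoughts and whose doctor does not know can leave by a yes to Q3, which does not ask about those thoughts, without the study-clinician step or the crisis text

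*Combined protocol and SAP*

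**What the plan says.** Section 6.2.3 (Participant Interview) contains two separate safeguards.

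**Score rule.** If the PHQ-9 total is 20 or more, or the PCL total is 30 or more, "the participant will be notified and advised to contact his/her physician or to visit the emergency department".

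**Item 9 script.** If item 9 is answered above the lowest category, the coordinator asks in turn:

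- Q1: "Let me ask another question, have you thought of hurting yourself in any way"
- Q2, after a yes at Q1: "Does your doctor know about this"
- Q3, after a no at Q2: "Have you talked to another clinician, like a counselor or psychologist, about how you have been feeling lately"

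A no at Q1, a yes at Q2 and a yes at Q3 all lead to the same reply, which includes "You should talk to your doctor about these thoughts, as you may benefit from treatment for depression". The interview then goes on. Only after a no at Q3, in person or by phone, does the coordinator offer contact with a study clinician and read the sentence that begins "If you are having thoughts of hurting yourself, the best thing to do is to go to the emergency department" and goes on to give the crisis line.

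The PHQ-9 and PCL are scheduled at T0 and T4 (Appendix C; Sections 6.2.3 and 6.3.5). They are not part of the T3 telephone interview (Section 6.3.4, Participant Interviews at T3).

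**The concern.** The script sorts participants by whether a clinician already knows of the self-harm thoughts. Q2 does this directly, because it follows Q1 and refers back to it. Q3 does not. It asks about recent feelings in general, so a participant who has seen a counselor about low mood, sleep or pain can truthfully say yes although no clinician has heard of the thoughts.

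That participant has just confirmed such thoughts and said that the doctor does not know. A coordinator who keeps to the script would give advice to see a doctor and carry on. The study-clinician step and the crisis sentence, both already written into the script, would be skipped. The script has the interviewer say that they are not a clinician, so its wording should not depend on improvisation.

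What is at stake is the safety of individual participants. No endpoint, power calculation or error rate is touched.

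**Working it through.** The plan gives no figure to reproduce. The check is a trace of the branches, followed by a look at whether another safeguard covers the gap.

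**1. End points of the script (Section 6.2.3)**

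| Answers | Doctor knows of the thoughts? | Study clinician offered | Crisis sentence read |
|---|---|---|---|
| Q1 no | not asked | no | no |
| Q1 yes, Q2 yes | yes | no | no |
| Q1 yes, Q2 no, Q3 yes | no; another clinician may or may not know | no | no |
| Q1 yes, Q2 no, Q3 no, in person | no | yes | yes |
| Q1 yes, Q2 no, Q3 no, by phone | no | yes | yes |

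There are five end points, and four follow confirmed self-harm thoughts. Two of those four carry the crisis sentence. Of the two that do not, a yes at Q2 means that a doctor is aware. A yes at Q3 carries no such assurance.

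**2. Does the score rule cover a yes at Q3?** It misses a participant only if both totals are below threshold, that is, PHQ-9 of 19 or less and PCL of 29 or less.

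- *PHQ-9 limb.* Section 6.4.2 says that depression "will be assessed using the nine item depression scale of the Patient Health Questionnaire". Item scoring is not stated; I assume 0 to 3. The largest total below threshold is 19. With item 9 at 1, 2 or 3, the other eight items can total 19 − 1 = 18, 19 − 2 = 17 or 19 − 3 = 16, out of a maximum of 8 × 3 = 24, without triggering the rule.
- *PCL limb.* Section 6.4.2 says that post-traumatic stress "will be measured using the standard PTSD Checklist (PCL), a 17-item measure". Item scoring is again not stated. Under 1 to 5 or 0 to 4, a total of 30 is a mean of 30 / 17 = 1.76 per item. Under 1 to 5 the floor is 17 × 1 = 17, so the threshold lies 30 − 17 = 13 points above it, and a 2 on every item (17 × 2 = 34) already triggers the rule.

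So the PHQ-9 limb can be missed even at the highest answer to item 9. The PCL limb, with its low threshold, may catch many whom the PHQ-9 limb misses. Neither limb depends on item 9, so coverage is not guaranteed. Where the rule does apply, it gives emergency-department advice but no crisis line.

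**3. Do the other sections cover it?** Sections 8.1.1 and 8.2.1 define adverse events and have them recorded at study visits. They link no action to item 9 and put no crisis text before the participant. The surgeon's assessment at enrollment (Section 6.1.2) and the clinical assessment at T4 (Section 6.3.2) bring clinician contact, but neither is tied to item 9.

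**4. How many are affected?** The documents give no rate for a positive item 9 or for any later answer, so no number can be derived.

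**The case against.** The strongest case against has four parts.

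- *Q3 in context.* The three questions run on from one another, and the next branch uses the same kind of language about feelings to refer to the disclosed thoughts. Many participants will hear Q3 as being about those thoughts. That stands, and it lowers the likely frequency of the problem. But the wording does not require that reading.
- *The exit is not empty.* After a yes at Q3 the participant is urged to tell the doctor, which answers the gap just disclosed. That also stands. It is still less than the same script gives after a no at Q3, where the participant also hears what to do if such thoughts are present.
- *Narrow exposure.* The PHQ-9 is scheduled only at T0 and T4, both study-center visits with clinicians at hand. That makes help easier to reach but does not prompt the coordinator to call for it.
- *Unseen documents.* The study-interviews appendix and draft case report forms listed in the contents, and the manual of operations cited in Section 11.1, were not available. The form that coordinators actually use may carry crisis text. This is why confidence is moderate.

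A reader might also infer that the yes exit at Q2 is defective because it too lacks the crisis sentence. The documents do not support that: Q2 establishes that a doctor knows of the thoughts, and returning such a participant to that doctor is defensible triage.

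**Conclusion.** The point holds for one path in the protocol-body script: yes at Q1, no at Q2, yes at Q3. On that path a participant can leave without the study-clinician step or the crisis text, because Q3 does not establish that the other clinician knows of the self-harm thoughts. The score rule reduces the gap without closing it.

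In size, it is one clear gap among the four end points after confirmed self-harm thoughts, affecting an unknown number of participants. The conclusion assumes that coordinators follow the script as written. The score-limb figures also rest on the assumed item scoring, but the branch trace does not.

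Two stronger readings should be avoided. It would be wrong to say that these participants never receive emergency advice, since those over either score threshold do. Nor do the documents show that investigators are not told or that nothing is logged, since the forms and manual that would settle this were not supplied.

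It is worth fixing as an inexpensive safety improvement, with moderate confidence.

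**What to change.** 1. Reword Q3 so that it names the thoughts, for example: *Have you told another clinician, such as a counselor or psychologist, about these thoughts of hurting yourself?* A participant whose other clinician does not know then answers no and goes to the existing study-clinician step.
2. After a yes at Q3, read the existing emergency-department and crisis-line sentence before the interview resumes. Rewording alone would remove most of the gap. The sentence adds protection for someone whose regular doctor still does not know.
3. Leave the order of questions, the no exit at Q1 and both no branches at Q3 as they are. Reading the same sentence after a yes at Q2 is an optional courtesy, not a correction.
4. Check the study-interviews appendix, case report forms and manual, and bring their script into line if it differs.

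The cost is one reworded question, one existing sentence used once more, a short script amendment through the review boards named in Section 12.1 and the Department of Defense route in Section 8.3.4, brief coordinator retraining at the three sites, and possibly a few more study-clinician conversations. No endpoint, visit or sample-size figure changes.

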6.3 Participant Follow up and Data Collection

The follow up visit schedule for this study will be closely related to the timing of brace fitting and PT participation. Follow up will occur immediately following post-IDEO PT (T2), 6 months following completion of all PT (i.e. post PRIORITI) (T3), and 12 Months post PRIORITI (T4). Each visit will have an interval of time surrounding the ideal date for the visit during which the visit may be completed and the data included in the trial database. This interval is approximately 1-2 weeks before or after the ideal date for a visit.

The data collected at follow-up are described below. These data are summarized in Appendix C.

6.3.1 Performance Assessments (at, T2, T4)

- 4 Square Step Test
- Illinois Agility Test
- Sit to Stand
- Timed Stair Ascent
- Self Selected Walking Speed
- Shuttle Run
- Single Leg Stance

6.3.2 Clinical Assessment at T4

- Weight
- ROM and Strength
- VAS Pain and Use of Narcotics

6.3.3 Participant Interviews at T2

- Use and Satisfaction with Brace (OPUS & CFI)
- Shoe wear and ambulatory aids

6.3.4 Participant Interviews at T3

- ALL ITEMS ASKED AT T2 PLUS:

- Short Musculoskeletal Function Assessment (SMFA)
- Veterans Health Survey (VR-12)
- Usual major activity status
- If working: Work Productivity (WPAI)
- Hospitalizations in past 6 months
- Use of Orthotic Services in past 6 months
- Use of PT/OT Services in past 6 months
- Use of other Services in past 6 months

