Following 2-4 weeks of home PT (T1), the participant will be fitted with the IDEO and engage in four weeks of Post-IDEO PT at the study center. During these 4 weeks, adjustments to the brace will be made and the participants will learn how to optimize the use of the brace.

At the end of the four weeks of post-IDEO PT (T2), performance testing will be repeated and overall satisfaction with the device assessed. The purpose of these assessments is to measure any immediate gains in function. Participants will then be formally ‘discharged’ from the PRIORITI program. They will be given the number of the Study Site Orthotist to call if any concerns arise with the IDEO and its fit. The costs associated with all visits to the orthotist during the 12 month follow-up period will be covered by the study.

At 6 months following the completion of the PRIORITI program (T3), participants will be contacted by the Study Coordinator and asked to participate in a brief interview by phone. The main purpose of this phone call is to keep participants engaged in the study and motivate them to come back to the hospital for the final visit at 12 months. We will also use this opportunity to ask them questions about their functioning, satisfaction with the brace and use of services (overall and specific to the IDEO). This interview will last about 15 minutes. During the call the he coordinator will remind the participant of the 12 month follow up visit. If the participant is living outside of the research site area, the coordinator will inform the participant that travel expenses can be covered for the 12 month follow up visit. (See appendix K).

At 12 months following the completion of the PRIORITI program (T4), participants will be asked to return to the Study Center to repeat the performance tests and self reported measures of outcome and satisfaction with the IDEO. Additional questions regarding use of services (overall and specific to the IDEO) will also be asked.

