6.3.5 Participant Interviews at T4

- ALL ITEMS ASKED AT T3 PLUS:
- Income (past year)
- Health Insurance (current)
- Self Efficacy
- Multidimensional Scale of Perceived Support (MSPS)
- Activities- Paffenbarger Activity Scale (PPAQ)
- Brief Pain Inventory (BPI)
- Patient Health Questionnaire Dépression Scale (PHQ-9)
- Post Traumatic Stress Disorder using the PCL Checklist

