the PRIORITI program could also improve relative to SOC and this has economic benefit from both the patient and societal perspectives.

Our analysis of the costs and benefits of PRIORITI will involve two components: (1) analysis of costs and outcomes as observed during the 12-month study period; and (2) cost-effectiveness projected over the patient lifetime. 12 Month Costs and Outcomes Difference in one-year cost for the PRIORITI group relative to standard of care will be evaluated based on difference in means. Confidence intervals for difference will be estimated using a bootstrapping procedure that is robust for the anticipated right-skewed distribution of costs. If average cost is greater for the PRIORITI group, a cost-effectiveness ratio will be calculated using a metric such as incremental cost per unit change in Short Form Musculoskeletal Function Assessment (SMFA), or incremental cost per unit change in VR-12.

Lifetime Cost-Effectiveness. If superior to standard care, the PRIORITI program could have a major impact on the patient's long-term functional status and quality of life. To gain insight on this proposition, a cost-effectiveness model will be constructed that simulates the long-term course for two identical patient cohorts, IDEO and standard of care. Model parameters will be derived from the study data, literature review, and expert opinion. Markov modeling will be used in order to characterize patient health state over time. For example, a small portion of patients who initially undergo limb reconstruction, later elect amputation. This would represent a change of "health state" in a Markov model and the probability of transition from the "limb reconstruction state" to "amputation state" will be derived from literature review. Similarly, patient preference (utility) for various health states associated with recovery from traumatic injury will also be estimated and used to calculate quality-adjusted life years, to be derived using the VR-6D. Overall findings of this analysis will be stated in terms of incremental cost per quality adjusted life-year for PRIORITI relative to standard of care.

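### No service-use question covers the 6-8 weeks from T0 to T2, so care received outside the programme in those weeks cannot be costed under Aim 4

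*Combined protocol and SAP*

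**What the plan says.** **Baseline.** Section 6.2.3 (Participant Interview) includes "Hospitalizations in Past Year" and asks about orthotic, PT/OT and other injury-related services over the same year.

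**Programme weeks.** Section 4 sets out the course: "Following 2-4 weeks of home PT (T1), the participant will be fitted with the IDEO and engage in four weeks of Post-IDEO PT". T2 is the end of those four weeks.

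**T2.** Section 6.3.3 lists "Use and Satisfaction with Brace (OPUS & CFI" together with shoe wear and ambulatory aids, and nothing on service use.

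**T3.** Section 6.3 places this contact "6 months following completion of all PT (i.e. post PRIORITI) (T3". Section 6.3.4 (Participant Interviews at T3) asks the four service items, beginning with "Hospitalizations in past 6 months".

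**T4.** Section 6.3.5 (Participant Interviews at T4) opens with "ALL ITEMS ASKED AT T3 PLUS". No separate recall period is given, so six months is inferred.

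**Schedule.** Appendix C agrees with the text. All four service rows are marked at baseline, T3 and T4 and are blank at T2. It has no T1 column, but it does list treatment logs kept by the CPO and the physical therapists.

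**Cost analysis.** Section 10.6, under Specific Aim #4, describes "analysis of costs and outcomes as observed during the 12-month study period". It does not say when the twelve months start, and it names no claims, billing or medical-record source for service use.

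**The concern.** Aim 4 is meant to measure what a year of taking part in PRIORITI costs and to compare that with projected standard of care. The programme itself runs from T0 to T2, and participants are discharged from it at T2. Those are the weeks for which the interviews ask nothing about hospital stays, therapy or orthotic visits outside the study, or other injury-related services.

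The undefined start of the cost period does not remove the difficulty:

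- If the year starts at T0, part of it has no service-use question.
- If it starts at T2, the two six-month recalls cover it, but the programme weeks fall outside the costed year. Only the logs could then bring programme costs back in.

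On either reading, non-programme care during the intervention is not collected by interview. Under section 10.6 the observed average cost decides whether a cost-effectiveness ratio is calculated, and study data also feed the lifetime model. The item can be collected cheaply at the time and less reliably afterwards.

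**Working it through.** The plan gives no figure of its own to reproduce. The check is timeline arithmetic.

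**Inputs**

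- Home PT before fitting: 2-4 weeks (section 4).
- Clinic PT after fitting: 4 weeks (section 4).
- T3 and T4: 6 and 12 months after the end of PT (section 6.3), taken as 26 and 52 weeks.
- Recall: one year at T0; six months at T3; six months at T4 (inferred).
- Visit window: "This interval is approximately 1-2 weeks before or after the ideal date for a visit" (section 6.3).

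**Length of the programme**

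T0 to T2 = (2 to 4) + 4 = 6 to 8 weeks.

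**Recall periods laid end to end**

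| Asked at | Period covered |
|---|---|
| T0 | the year before T0 |
| T2 | none |
| T3 | T2 to T3 |
| T4 | T3 to T4 |

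The uncovered stretch is T0 to T2.

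**Share of time**

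- T0 to T4 = (6 to 8) + 52 = 58 to 60 weeks.
- Uncovered share = 6/58 = 10.3% to 8/60 = 13.3%.
- If the cost year is counted as 52 weeks from T0: 6/52 = 11.5% to 8/52 = 15.4%.

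**Effect of the visit window**

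The T3 recall is tied to the interview date. With a gap of g weeks at nominal dates and T3 held w weeks late (negative if early), the gap is g + w. The extremes are 6 - 2 = 4 weeks and 8 + 2 = 10 weeks.

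**From time to cost**

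Let weekly non-programme cost be r after T2 and k × r between T0 and T2. The share of non-programme cost missed over T0 to T4 is k × g / (k × g + 52). With k = 1 this is the 10.3% to 13.3% above. It is smaller if k is below 1 and larger if k is above 1. The documents give no service-use rates, so k is unknown. The formula also leaves out the device, fitting and study PT, so it is not a share of total PRIORITI cost.

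**After the change**

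With the four items asked at T2 for the time since T0, the uncovered time is 0 at nominal dates. A T3 call held late would still leave up to 2 weeks after T2 unasked.

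**The case against.** **The records already kept cover these weeks.** Section 7.2 requires the therapy at each session to be documented, Appendix C lists CPO and PT logs, and brace adjustments in the four post-fitting weeks are part of the programme. This stands for study therapy and brace work, probably the largest items. The fields of the logs are not shown, and nothing indicates that they record outside therapy, hospital stays or other services.

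**Adverse event forms would show hospitalisations.** Section 8.2.1 has events recorded at study visits whether or not they are related to the study, so some would appear. But these forms are not named as a cost source and would miss routine visits. Section 8.1.3 does not make hospitalisation a criterion for seriousness, and section 8.3.1 lets a site report some events only locally.

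**The cost year may simply be T2 to T4.** Section 4 does speak of a twelve-month follow-up after discharge, and the recalls cover that period. It would, however, exclude the programme weeks from an aim that concerns the cost of participation.

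**The question wording has not been seen.** The draft case report forms and interviews in the list of appendices are not in the text reviewed. That caution is fair, although section 6.3 and Appendix C agree with each other.

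**A stronger reading does not stand.** A reader might infer that PRIORITI's cost is understated by 10-13% or more, in the programme's favour, because care peaks in these weeks. The documents do not support that:

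- They give no rates. Use could be lower in these weeks, since people with surgery on the study limb anticipated within six months are excluded and supervised PT three times a week may displace outside PT.
- The first 2-4 weeks come before fitting, so care arising from the IDEO cannot occur then.
- The comparator is a projection with no stated time window, so bias in the difference cannot be signed.

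**Conclusion.** The gap is real and appears in both the text and the schedule: 6-8 weeks, or 10-13% of T0-T4 time at nominal dates, without a service-use question. This rests on the T4 recall being six months and on the interviews following the protocol's lists.

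If T0-T2 belongs in the cost of participating, that cost omits non-programme care in those weeks. The omission can only lower PRIORITI's own cost, by an amount the documents do not let one size. The 10-13% becomes a cost share only for non-programme services, and only if their use is assumed constant over time.

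The matter is minor. Aim 4 is secondary and descriptive, and no efficacy endpoint is affected.

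**What to change.** 1. Add the four existing service-use items (hospitalisations, orthotic, PT/OT, other) to the T2 interview in section 6.3.3 and mark them at T2 in Appendix C. Word them to cover the time since the first study visit, not counting study PT and study orthotist visits, so that logged sessions are not counted twice.
2. State in section 10.6 that PRIORITI costs are counted from T0, with study-provided services taken from the CPO and PT logs.

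**Cost.** A few extra minutes at an existing visit and a small change to one form.

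Lengthening the T3 recall back to T0 would also close the gap, but it is the weaker choice. It asks participants to remember 26 + (6 to 8) = 32 to 34 weeks during a call planned for about 15 minutes. It would also draw logged study sessions into self-report unless they were excluded.
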